18.01 Data Safety Monitoring II

A designee will perform the safety monitoring:

Yes No

Identify the designee [provide contact information]:

A medical monitor or independent individual/safety officer will be performing the safety assessments.

Yes No

Identify who will be performing the safety assessments [provide contact information]:

[name]
Professor of Pediatrics and Reproductive Biology
Case Western Reserve University School of Medicine
Director of the Division of Neonatology
MetroHealth Medical Center
[name]
[name]
[contact]
email: [contact]

Has a Data Safety Monitoring Board or Committee been established for this study?

Yes No

Identify these members by name, title and qualifications. How often will the DSMB meet? How frequently will the DSMB report it's findings?) data prior to 9/28/2010 read only.

If there is a DSMB or DSMC is it a nationally constituted Data and Safety Monitoring Committee? Yes No

Please enter the Name of Contact or Chair, Address and Phone or E-Mail:

Is there a locally constituted Data and Safety Monitoring Committee or Board that will perform the safety monitoring. Specify composition and responsibilities in the box below. Note: Board Members should not have conflicts with this study or with study personnel. Yes No

Names of Members of Local DSMB [provide contact information]:

3.B.1 Description of anticipated adverse events. Pulled from question 10.5.

Targeted fortification- rare, some babies may have elevated BUN which is routinely monitored in the NICU, or rare, feeding intolerance

There is also risk of breach of confidentiality, but this is rare. Data will be stored securely, only key study investigators will have access to data, and it will be deidentified and only the PI will have access to the key.

The probability and magnitude of harm or discomfort anticipated in the research are no greater than those ordinarily encountered daily during routine care while admitted to NICU.

Additional Comments on anticipated adverse events:

3.B.2 Safety data/procedure used to preform evaluation:

Data to be evaluated:

Name

There are no items to display

Who will evaluate safety data:

Frequency of Monitoring:

Name

6 Months

3.C. Grading method and attribution for adverse event reporting:

Grading method and attribution for adverse event reporting

The PI must identify what scale will be used to grade adverse events (AEs) and indicate his/her attribution/assessment of the relationship between the adverse event and the protocol/intervention. Each protocol may have a unique approach to grading adverse events and the PI should consult the parent protocol and/or funding source for specific grading scales. Suggested guidelines for the grading of adverse events are available below:

Example A: Cancer Therapy Evaluation Program (CTEP) Common Toxicity Criteria (CTC II) available for viewing at <http://ctep.info.nih.gov> (see "Reporting Guidelines, Common Toxicity Criteria")

Example B: Common grading scale

0	No adverse event or within normal limits or not clinically significant
1	Mild AE, did not require treatment
2	Moderate AE, resolved with treatment
3	Severe AE, resulted in inability to carry on normal activities and required professional medical attention
4	Life threatening or disabling AE
5	Fatal AE

3.C.1 Identify the scale to be used to Grade AEs in this study:

CRU Safety Scale:

Name

There are no items to display

3.C.2 Identify the attribution scale to be used in this study:

CRU Attribution Scale:

Name

There are no items to display

3.D. Population being studied: (populated from your answers to Sections 11.00 and 12.00)

Vulnerable subject groups? Yes

Children? Yes

Decisionally Impaired Subjects? No

Pregnant Women and/or Fetuses? No

Will you be enrolling Prisoners? No

Other Populations being studied:

Vulnerable Populations[Poor / Uninsured](#)[Minors - Children under 18](#)[Employees](#)[Students](#)[Minorities](#)

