This will be a prospective randomized control study of preterm infants less than 1500 grams [very low birth weight (VLBW)] receiving human milk (maternal or donor) will be included. The control group will receive adjustment of total parenteral nutrition (TPN) per NICU guidelines as enteral feedings are advanced followed by standard fortification of human milk. The intervention group will have TPN (protein and lipids) adjusted based on analysis of human milk as feedings are advanced to provide goal 4g/kg/day of protein and 100-130 kcal/kg/day followed by targeted fortification of breast milk based on human milk analysis to continue to provide 4 g/kg/day of protein and 100-130 kcal/kg/day for once full feeds are achieved. The primary aim of this study is to evaluate the growth, anthropometric measurements, and body composition, to see if targeted fortification improves neonatal growth. By optimizing neonatal growth and nutrition there is potential to also have an impact on other morbidities and long term neurodevelopmental outcomes.

This is your abstract also known as a synopsis from an industry sponsored study. Please limit to 500 words.

7.2 * **What are the specific aims of this study i.e. what are the question(s) this research intends to answer? Provide at a maximum 3 primary and 3 secondary aims.**

The aim of this study is to demonstrate improved growth and body composition in VLBW infants by using human milk analysis as a tool to guide when adjusting TPN and lipids followed by targeted fortification of breast milk at full feeds to provide 4g/kg/day of protein 100-130 kcal/kg/day, compared to those who receive standard management of TPN per guidelines and standard fortification.

The primary outcome measured will be body composition measurement 4 weeks after achieving full feeds with targeted fortification, or at NICU discharge, whichever comes first.

Secondary outcome variables:

1) Weight gain velocity

2) Anthropometric measurements including weight, length, head circumference, and mid upper arm circumference or skinfold thickness

This is your Hypothesis also know as your aims (NIH) or safety and efficacy aims (industry). Please list no more than 3 primary and 3 secondary clearly label these aims primary and secondary.

7.3 **Please provide a summary of the present knowledge relevant to the research and make citation to any applicable scientific literature:**

This is your literature search and bibliography. Also known as

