- Mothers collect a 24hr supply of breast milk once per week, from which a study team member will obtain a 10 ml representative sample for analysis. The 24hr collection of breast milk will be mixed into a clean container that can accommodate the entire volume. It will be homogenized and a 10 ml sample removed for

analysis. The remaining breast milk will be repackaged and placed back into the refrigerator in the NICU.

- After analysis, the milk for the following 1 week will be labeled and batched together
- For donor breast milk, each 'lot' will be analyzed and labeled for future use
- Analysis will take place at MetroHealth in the lab, using the Miris human milk analyzer. The amount of fat (grams), lactose (grams), total protein (grams), true protein (grams), and energy (kcal) per 100 ml will be reported and used for calculations.
- Infants will have birth measurements obtained, daily weight, weekly anthropometric measurements, and body composition measurement prior to discharge. The measurements will take a few minutes to obtain on routine basis per NICU protocol. The Peapod (body composition) measurement will take approximately 20 minutes total traveling from the NICU to CRU and back, but the actual assessment takes 2-3 minutes. This will be done with the infant is medically stable and approaching discharge.

The subjects will be in the study from time of consent to 4 weeks following the achievement of full enteral feedings, which may range from 6 weeks to 12 weeks depending on the birth weight and the clinical status of the infant. The smallest babies will take the longest to increase to full feeds due to the slow feeding protocol.

8.7 Please attach study design/subject visit schedule here:

Name	Description
There are no items to display	

If you have an electronic schedule of study visits and/or procedures please attach here.

View: 09-00 Inclusion/Exclusion Criteria

9.0 Inclusion/Exclusion Criteria:

9.1 What are the inclusion criteria? Put this information in bullet form:

Premature infants <1500 g
Mother consenting to provide breast milk or use of donor breast milk

Please list inclusion criteria.

9.2 What are exclusion criteria? Put this information in bullet form:

Infants with major congenital malformations
Infants with medical conditions precluding them from having breast milk
Mothers with medical conditions that preclude them from providing breast milk
Insufficient breast milk supply
Refusal of donor breast milk

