10.2 Describe any therapeutic alternatives to the research that may exist. How are they different from those procedures that subjects would normally undergo?

Therapeutic alternative is standard fortification of breast milk per protocol. This uses reported average protein and caloric content of breast milk and adds standard amounts of fortifier. Content of breast milk is variable between mothers and has wide range. They also have the option to not participate in the study and receive standard NICU management.

Describe any therapeutic alternatives. Can subjects receive this drug or device outside of a research study?

10.3 What are the outcome variables and how will they be analyzed? What are the statistical and analytical methods that will be used? Note this section can be copied from the NIH Grant Application or from the Statistical and Analytical Methods section of the industry trial protocol.

The outcome variables are the anthropometric measurements including daily weight; weekly length, head circumference, skin fold thickness or mid upper arm circumference; and PEAPOD body composition measurements prior to discharge.

Define outcomes and describe data analysis, please include a power calculation.

Our primary outcome is body composition, as measured by air displacement plethysmography (PEAPod). As standardized assessment of body composition is relatively new in the preterm infant population, we are using clinical judgment to determine that a difference in fat free mass z-score (from data from Norris T, 2019) of 0.5 is clinically significant. To detect a difference at alpha $\alpha=0.05$ with 80% power, 25 infants per group are required. This is a realistic goal for clinical enrollment, due to the historical MetroHealth NICU census composition. According to the census at MetroHealth, the total number of infants with birth weight less than 1500 g for 2016 was 81 infants, and in 2017 was 84 infants.

If the requested information does not fit in the text box please attach a word document.

10.4 If the above requested information does not fit in the text box please attach a word document here:

Name	Description
There are no items to display	

View: 10-01 Risk/Benefits

10.1 Assessment of Risk II:

10.5 List and quantitate the risks involved for each experimental procedure in bullet form. Identify risks as common (greater than 10%) uncommon (greater than 1% up to and including 10 %) rare (1% or less). This must match the risks listed in the Consent Form:

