In this research, infants are given additional protein and fat targeted to their mother's breast milk composition and their nutritional needs, which alone does not have any potential risk. The benefit of improved growth is significant with overall improved medical and neurodevelopmental outcomes. Potential benefits outweigh the risk of participation.

Discuss why the risks are reasonable in relation to the anticipated benefits.

- 10.15 Attach Documents:**

Name	Description
There are no items to display	

Attach documents here.

View: 11-00 Study Participant Information I

11.0 Study Participant Information I:

- 11.1 How will the Principal Investigator assure he/she has access to a population that would allow recruitment of the required number of study participants (i.e. prep for research):**

Based on MetroHealth Medical Center NICU statistics, there are approximately 80 babies weighing less than 1500 grams admitted every year.

How does the PI know he/she has the required number of subjects?

The accrual numbers in 11.2 represent mother/baby couples.

- 11.2 Anticipated number of subjects (all sites): [enter a number]**

60

Please give the total # of subjects to be enrolled at all sites and anticipated subjects to be enrolled at MHS.

Anticipated number of subjects to be enrolled at MHS: [enter a number]

60

Anticipated number of potential subjects to be approached: [enter a number]

60

- 11.3 If this is a multi-site study, how many sites will there be? [enter a number]**

How many total sites?

- 11.4 Subject Characteristics:**

Subject Population Categories

[Inpatients](#)

Check all that apply

- 11.5 Subject Source:**

Subject Source Characteristics

[Other](#)

Check all that apply

11.6

If "other" list above in either 11.4 or 11.5 please describe:

Infants delivered at MHMC with birth weight less than 1500 grams on admission to NICU.

If applicable please describe.

View: 12-00 Study Participant Information II

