We are not introducing a new drug. We are only adjusting the amount of protein and fat given to premature infants based on the analysis of their mother's breast milk composition in the intervention group. Outcomes measured are growth parameters and anthropometric measurements when infants are clinically stable. The harm anticipated is no higher than those encountered in daily life or during care in the NICU, therefore only needing low level monitoring.

High Level of Monitoring

Justification for selecting Risk High Level of Monitoring:

View: 18-01 Data Safety Monitoring II

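### The plan names elevated BUN and feeding intolerance as risks of targeted fortification but sets no comparison of either between the arms

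*Combined protocol and SAP*

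**What the plan says.** **Risks.** Section 10.5, repeated in Section 18.01 item 3.B.1, attaches two harms to targeted fortification: "some babies may have elevated BUN which is routinely monitored in the NICU, or rare, feeding intolerance". Both are classed as rare, which the form defines as 1% or less.

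**Outcomes.** Section 7.2 makes body composition primary, with weight gain velocity and "Anthropometric measurements including weight, length, head circumference, and mid upper arm circumference or skinfold thickness" as secondary. Section 10.3 opens with "The outcome variables are the anthropometric measurements including daily weight; weekly length, head circumference, skin fold thickness or mid upper arm circumference" and adds the PEAPOD measurement. Section 14.1B gives the same list as the purpose of data collection. The safety plan (Section 18.0, monitoring-level justification) says "Outcomes measured are growth parameters and anthropometric measurements when infants are clinically stable".

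**Safety review.** In Section 18.01, item 3.B.2 shows an empty list of data to be evaluated and a monitoring frequency of 6 months. Items 3.C.1 and 3.C.2 select no grading or attribution scale. A person is named for safety assessments. Item 4.A sends anticipated and unanticipated reportable events to the IRB. Sections 10.6 and 4.B make intolerance, emesis and distention grounds for stopping, and allow removal for acute decompensation.

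**Duration.** Section 8.6 gives participation as running from consent to 4 weeks after full feeds, "which may range from 6 weeks to 12 weeks depending on the birth weight and the clinical status of the infant".

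**Benefit and risk.** Section 10.14 says of the added protein and fat "which alone does not have any potential risk" and concludes that potential benefits outweigh the risk.

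**The concern.** The intervention delivers extra protein and fat, and the plan itself says what could go wrong. A trial that measures only growth informs one side of the balance. Section 10.13 says that, if a significant difference is shown, milk analysis and targeted fortification could become standard of care. A reader deciding on that step would want to know whether BUN ran higher, or feeds were stopped more often, in the targeted arm. Followed exactly as written, the plan produces no such table. Its one periodic look at safety is spaced more widely than any infant's time in the study.

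**Working it through.** **1. The plan's own figure.** No safety figure is stated. The only computed figure is 25 per group for a 0.5 difference in fat-free-mass z-score. No SD is given, so it cannot be reproduced from stated inputs. With n = 2(1.96 + 0.842)² SD² / 0.5², it needs SD of about 0.63 (two-sided). That is a separate matter; here 25 serves only as an arm size, alongside 30 (60 mother/baby couples at 1:1).

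**2. Tracing each named harm through the plan.**

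| | BUN | Feeding intolerance |
|---|---|---|
| Named as a risk (10.5, 3.B.1) | yes | yes |
| Outcome (7.2, 10.3, 14.1B, 18.0) | no | no |
| Data to be evaluated (3.B.2) | no | no |
| Stopping or removal criterion (10.6, 4.B) | no | yes, without a threshold |
| Measured or noticed in routine care | yes | yes |
| Comparison by arm | none stated | none stated |

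**3. Review interval against participation.** Take 6 months as 26 weeks, counted from first enrolment (an assumption).

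- Longest stated participation: 26 − 12 = 14 weeks. Every infant enrolled in the first 14 weeks, a little over 3 months, has finished before the first review.
- Shortest: 26 − 6 = 20 weeks.
- The anticipated dates, 5/20/2019 to 3/31/2021, span 681 days, or 97.3 weeks. Assuming uniform accrual of 60 over that span, 60 × 14 / 97.3 = 8.6 couples enrol in the first 14 weeks. If enrolment closes 12 weeks before the end date, the figure is 60 × 14 / 85.3 = 9.8.
- In any later cycle under uniform accrual, the share of that cycle's infants still in the study at the review is 6/26 = 23% to 12/26 = 46%.
- The CRU section gives about 90 inpatient days per subject. That too is shorter than 6 months.

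**4. What a by-arm table could show.**

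- Chance of at least one event in an arm at a true rate of 1%: 1 − 0.99²⁵ = 22%; 1 − 0.99³⁰ = 26%.
- Upper one-sided 95% bound after zero events: 1 − 0.05^(1/25) = 11.3%; 1 − 0.05^(1/30) = 9.5%.
- Power at 30 per arm for illustrative, assumed rates: 1% v 10%, 33%; 5% v 20%, 42%; 10% v 30%, 49%.

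The table would be descriptive. These limits hold with or without the change, so they govern how the table is worded; they do not measure the gap in the plan.

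**5. Sections 10.5 and 10.14.** Section 10.5 lists two risks of targeted fortification. Section 10.14 says the added protein and fat alone carry none. Both statements cannot stand.

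**The case against.** The strongest reply is that infants are protected and the data exist. BUN is measured routinely, intolerance triggers stopping, reportable events go to the IRB in a timely manner, and a safety assessor is named. Section 14.3 draws prospective data from the electronic record. The attached data collection sheet is not visible and may hold BUN, tolerance or withdrawal fields. All of this stands, and it limits what can be said.

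- A reader might infer that the trial *cannot* weigh these harms. The documents do not support that: charts hold BUN values, and staff would know of stops for intolerance. What is absent from the visible text is a plan to compare them.
- A reader might infer that removing affected infants hides a BUN imbalance. BUN is not a stopping or removal criterion, so no infant leaves for it under the stated rules.
- A reader might take the 9.5% bound as the size of the problem. It is the same after the change.

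It is also fair that the 6-month interval is a periodic review and that bedside care does not wait for it. The timing point concerns only whether the assessor sees accumulated data while infants are still in the study. The form itself notes that vulnerable populations may need more frequent monitoring.

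Finally, 10.13 is conditional on a significant difference, and 10.14 is a pre-study answer on an IRB form. Neither is a trial conclusion. Even so, case-by-case care and reporting do not amount to a comparison between arms.

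**Conclusion.** The point holds as an omission in the analysis and monitoring plan: two harms are named, and neither is set to be compared by arm in any visible text. It is worth fixing because it decides whether the trial can report anything about the risk side of its own balance.

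In size, the first review would come after every infant from about the first 14 weeks had finished, some 9 to 10 of 60 couples. At each later review at most 46% of that cycle's infants would still be in the study. These counts assume uniform accrual, reviews timed from first enrolment, and the stated 6 to 12 weeks. The absence of a planned comparison does not depend on them.

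What remains open is the unseen data sheet: it could show that the fields are collected, but the visible plan states no analysis or review that uses them. The contradiction between 10.14 and 10.5 stands on the text alone.

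**What to change.** Add to 10.3, as descriptive safety outcomes by arm for every randomised infant, including those stopped or removed:

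- **BUN** from routine draws, with the number of draws per infant. Caregivers are unblinded, so one arm could be tested more often, and a bare peak value rises with testing.
- **Feeding intolerance events**, with a definition set by the investigators before enrolment and applied identically in both arms. Section 10.6 gives terms but no thresholds.
- **Stops and removals**, with reason.

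Report these with confidence intervals, and state that 25 to 30 infants per arm cannot confirm a rate of 1% or less.

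List the same items in 3.B.2 for the named safety assessor, with a review interval short enough to allow action while infants are still in the study. Reconcile 10.14 with 10.5.

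The cost is a few chart fields already recorded in care and some short extra reviews by an assessor already in place. No feeding or treatment rule changes.

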*** Note More Frequent monitoring intervals may be needed for vulnerable populations.**

4.A. Plan for Adverse Event Reporting:

All Reportable Events (Anticipated and Unanticipated events) from this protocol must be submitted using the MHA eIRB Reportable event form in a timely maner consistent with MHS IRB SOPs.

In addition to the MHS IRB adverse events and Uanticipated problems will be reported to:

Reporting Institutions (check all that apply):

Name

There are no items to display

If other has been selected above please specify:

4.B Stopping Rules or Conditions under which Subjects can be removed from the Study [this information is from Section 10.01 of the Protocol Risks/Benefits Questions

Are there defined Stopping Rules? Yes

What are the stopping rules for the study? Intolerance to fortification, excessive emesis or recurrent, otherwise unexplained, abdominal distention.

What findings, events, or conditions would require a research subject to be removed from the study? (i.e. disease progression)

Clinical worsening, acute decompensation of infant precluding them from receiving enteral feeds.

If a patient become acutely ill and significantly decompensates they may be removed from the study. Ex: sepsis, abdominal distention, blood in the stool, respiratory failure with increasing need for respiratory support. If a patient becomes comfort-care only and no longer receiving enteral feeds they may also be removed from the study.

4.D. Additional Information (if Applicable):

Provide any other information relevant to the data and safety monitoring plan that was not already incorporated into this form.

Attach A copy of your Data Safety Monitoring Plan or other relevant information related to this form:

Name

Version

There are no items to display

View: 19-00 Use of Human Biological Materials In Research I

